8.1.1.3 TREATMENTS 1-20

Randomized subjects will undergo the first treatment session no later than 48 hours after randomization and within 4-21 days after stroke onset. Active or sham study intervention sessions using BQ 2.0 (active or sham therapy, respectively) will be conducted 5 times a week, for approximately 9 weeks and until completion of 45 treatment sessions, conducted in either inpatient, outpatient or home setting.

At each of these visits, the subject will undergo a study treatment. Each treatment session will last up to 60 minutes, with active or sham field being turned on for the first 40 minutes. During the session, subjects will be asked to perform a device guided, standardized, pre-defined and evidence-based PT/OT therapy activities, with approximately 30 minutes dedicated to the upper extremity and 30 minutes to the lower extremity, aligned with the Class 1 level A recommendation for patients with stroke to participate in a home-based rehabilitation program.

A trained member of the site study team (the “**Clinic Operator**”) will be responsible for training and approving the subject’s caregiver to operate the session independently.

²⁷ MRI images will be preferred over CT images

	The efficacy of a frequency-tuned electromagnetic field treatment in facilitating the recovery of subacute ischemic stroke patients – a pivotal study		
	No. BQ5	Ver. 4	Page 64 of 150

Before an approval to operate a session independently (the “**Approval**”) is granted by the Clinic Operator, a Clinic Operator will train the caregiver and supervise the sessions, either in-person or remotely. Once an Approval was granted, sessions will be conducted with the assistance of a caregiver while the Clinic Operator will provide periodic oversight (combined audio and video remote conferencing or audio only, if video is not available). If needed, and at their discretion, the Clinic Operator may join sessions following the Approval too.

At each of these visits, the following data will be collected:

- Any changes in concomitant medications
- Any adverse events
- Any device deficiencies
- Duration of stimulation delivered and number of pauses if occurred
- Duration of PT/OT activities performed during the 60-minute period
- PT/OT activities performed outside of study since last visit

8.1.1.4 MIDTERM FOLLOW-UP VISIT (IN CLINIC)

This visit will take place in the clinic (± 4 days from the 20th treatment). Though, in special circumstances and subject to the approval of the Principal Investigator, the visit can be conducted in an out-patient setup or via combined audio and video remote conferencing or audio only, if video is not available.

The following assessments (described in § 8.1) will be performed during this visit:

- mRS,
- FMA-UE,
- BBT,
- SIS Hand Domain,
- SIS-16

At this visit, the following data will be collected as well:

- Vital signs
- Any changes in concomitant medications
- Any adverse events
- Any device deficiencies
- PT/OT activities performed outside of study since last visit
- Use of healthcare resources

	The efficacy of a frequency-tuned electromagnetic field treatment in facilitating the recovery of subacute ischemic stroke patients – a pivotal study		
	No. BQ5	Ver. 4	Page 65 of 150

At this visit day, a treatment session may or may not take place, in accordance to the availability of the subject and/or the site. If a session will not take place, and unless completed over the weekend, 4 treatment sessions will take place in that week.

If a treatment session is to take place at the same day of the assessment, the session may be conducted only after the assessments were completed to avoid changing outcome measure scores due to subject fatigue.

8.1.1.5 TREATMENTS 21-45

At each of these visits, the subject will undergo a study treatment. Each treatment session will last up to 60 minutes, with active or sham field being turned on for the first 40 minutes. During the session, subjects will be asked to perform a device guided, standardized, pre-defined and evidence-based PT/OT with approximately 30 minutes dedicated to the upper extremity and 30 minutes to the lower extremity aligned with the Class 1 level A recommendation for patients with stroke to participate in a home-based rehabilitation program.

At each of these visits, the following data will be collected:

- Any changes in concomitant medications
- Any adverse events
- Any device deficiencies
- Duration of stimulation delivered and number of pauses if occurred
- Duration of PT/OT activities performed during the 60-minute period
- PT/OT activities performed outside of study since last visit

8.1.1.6 DAY 90 PRIMARY OUTCOME ASSESSMENT VISIT (IN CLINIC)

This visit will take place in the clinic. Though, in special circumstances and subject to the approval of the Principal Investigator, the visit can be conducted in an out-patient setup or via combined audio and video remote conferencing or audio only, if video is not available.

The following assessments (described in § 8.1) will be performed during this visit:

- mRS,
- FMA-UE,
- BBT,
- 10MWT
- SIS Hand Domain,
- SIS-16,

	The efficacy of a frequency-tuned electromagnetic field treatment in facilitating the recovery of subacute ischemic stroke patients – a pivotal study		
	No. BQ5	Ver. 4	Page 66 of 150

- EQ-5D-5L
- ALDS,
- MoCA,
- PHQ-8,

At this visit, the following data will be collected:

- Vital signs
- Any changes in concomitant medications
- Any adverse events
- Any device deficiencies
- PT/OT activities performed outside of study since last visit
- Use of healthcare resources

Additionally, at this visit, the subjects will be asked to rate their certainty regarding group allocation by selecting one of five options: (1) knew they had received active stimulation; (2) thought they received active stimulation; (3) knew they were in the sham stimulation group; (4) thought they were in the sham stimulation group; or (5) did not know which treatment group they were allocated.

8.1.1.7 DAY 180 ADDITIONAL FOLLOW-UP VISIT

This additional follow up will be conducted remotely via combined audio and video remote conferencing (or audio only, if video is not available), or in-person, if preferred.

The following assessments (described in § 8.1) will be performed during this visit:

- mRS
- SIS Hand Domain,
- EQ-5D-5L

At this visit, the following data will be collected:

- Any adverse events
- Any changes in concomitant medications
- Use of healthcare resources

8.2 SAFETY AND OTHER ASSESSMENTS

The following procedures/evaluations will be performed to assess safety in this study in addition to the descriptions already described above in this § 8.

Assessment of adherence to investigational product use. Please refer to § 6.4.

Assessment of adverse events. Adverse events will be assessed for severity, seriousness, expectedness, action taken, and relation to the study device and procedure and recorded at each study Visit, at which time the subject will provide data on all adverse events that occurred since the last Visit. Please refer to §§ 8.3.1, 8.3.4, 8.3.5, and 8.3.8 for adverse event definitions, period of reporting, reporting specifications, and events of special interest.

8.3 ADVERSE EVENTS AND SERIOUS ADVERSE EVENTS

8.3.1 DEFINITION OF ADVERSE EVENTS (AE)

Adverse event (AE) is any untoward medical occurrence, unintended disease or injury, or untoward clinical signs (including abnormal laboratory findings) in subjects, users or other persons, whether or not related to the investigational medical device and whether anticipated or unanticipated. This definition includes events related to the investigational medical device or the comparator²⁸. This definition includes events related to the procedures involved. For users or other persons, this definition is restricted to events related to investigational medical device or comparators.

AEs include any event having been absent at baseline, or, if present at baseline (medical history), subsequently worsening.

Adverse device effect (ADE) is an adverse event related to the use of an investigational medical device. This definition includes adverse events resulting from insufficient or inadequate instructions for use, deployment, implantation, installation, or operation, or any malfunction of the investigational medical device. This definition includes any event resulting from use error²⁹

²⁸ Comparator is a medical device, therapy (eg, active treatment, normal clinical practice), placebo or no treatment, used in the control group in a clinical investigation (ISO 14155:2020 § 3.12)

²⁹ ISO 14971:2019 (definition 3.30): user action or lack of user action while using the medical device that leads to a different result than that intended by the manufacturer or expected by the user. Use error includes the inability of the user to complete a task. Use errors can result from a mismatch between the characteristics of the user, user interface, task, or use environment. Users might be aware or unaware that a use error has occurred. An unexpected physiological response of the patient is not by itself considered use error. A malfunction of a medical device that causes an unexpected result is not considered a use error.

or from intentional misuse of the investigational medical device. This includes comparator if the comparator is a medical device.

Device deficiency is an inadequacy of a medical device with respect to its identity, quality, durability, reliability, *usability*, safety or performance. Device deficiencies include malfunctions, use errors, and inadequacy in the information supplied by the manufacturer including labelling. *This definition includes device deficiencies related to the investigational medical device or the comparator.*³⁰

8.3.2 DEFINITION OF SERIOUS ADVERSE EVENTS (SAE)

Serious adverse device effect (SADE) is an adverse device effect that has resulted in any of the consequences characteristic of a serious adverse event.

Serious adverse event (SAE) is an adverse event that led to any of the following

- a. death,
- b. serious deterioration in the health of the subject, *users or other persons* as defined by one or more of the following:
 - 1. a life-threatening illness or injury, or
 - 2. a permanent impairment of a body structure or a body function including chronic diseases, or
 - 3. in-patient or prolonged hospitalization, or
 - 4. medical or surgical intervention to prevent life-threatening illness or injury or permanent impairment to a body structure or a body function,
- c. fetal distress, fetal death or a congenital abnormality or birth defect including physical or mental impairment

NOTE: Planned hospitalization for a pre-existing condition, or a procedure required by the clinical investigation protocol, without serious deterioration in health, is not considered a serious adverse event.

8.3.3 CLASSIFICATION OF AN ADVERSE EVENT

³⁰ The part of the device deficiency definition appearing in italics is introduced in ISO 14155:2020 and is absent from the definition available in CHAPTER I Article 2(59) of the MDR. For the purposes of this trial, the definition in this protocol will apply for Investigator reports to the Sponsor. Applicability of the gap between the definitions in this protocol and the aforementioned MDR definition will be assessed for Sponsor reports to National Competent Authorities if and where MDR will apply to this trial.

8.3.3.1 SEVERITY OF EVENT

All events will be graded according to the National Cancer Institute Common Terminology Criteria for Adverse Events (NCI CTCAE) Version 5.0 available on:

https://evs.nci.nih.gov/ftp1/CTCAE/CTCAE_5.0/

Grade refers to the severity of the AE. The CTCAE v.5.0 displays Grades 1 through 5 with unique clinical descriptions of severity for certain AEs based on a general guideline shown in [Table 3](#) below.

Table 3. NCI CTCAE v.5.0 grading system

Grade 1	Mild	Asymptomatic or mild symptoms; clinical or diagnostic observations only; intervention not indicated.
Grade 2	Moderate	Minimal, local or noninvasive intervention indicated; limiting age-appropriate instrumental ADL*.
Grade 3	Severe or medically significant but not immediately life-threatening;	Hospitalization or prolongation of hospitalization indicated; disabling; limiting self-care ADL**.
Grade 4	Life-threatening consequences	Urgent intervention indicated.
Grade 5	Death related to AE.	

*Instrumental ADL (Activities of Daily Living) refer to preparing meals, shopping for groceries or clothes, using the telephone, managing money, etc.

**Self-care ADL refer to bathing, dressing and undressing, feeding self, using the toilet, taking medications, and not bedridden.

For events not listed in the CTCAE toxicity table, severity should be assessed using the general CTCAE grading guideline provided in [Table 3](#).

8.3.3.2 RELATIONSHIP TO STUDY INTERVENTION

For all collected AEs, the Investigator who examines and evaluates the subject will provide the Sponsor with his/her assessment of the AE causality based on temporal relationship and his/her clinical judgment³¹. The degree of certainty about causality will be graded using the categories in [Table 4](#) below³².

³¹ Procedure related events refers to the procedure related to the initial application of the investigational medical device only and therefore not to any other procedures or treatments applied later throughout the clinical investigation, for instance to treat (serious) adverse events (MEDDEV 2.7/3 revision 3 - GUIDELINES ON MEDICAL DEVICES - CLINICAL INVESTIGATIONS: SERIOUS ADVERSE EVENT REPORTING UNDER DIRECTIVES 90/385/EEC AND 93/42/EEC)

³² Based on the EU medical device coordination group (MDCG) guidance 2020-10/1 *Safety reporting in clinical investigations of medical devices under the Regulation (EU) 2017/745*. Although originally proposed for serious adverse events, it is suitable for non-serious events as well.

The Sponsor and the Investigators will distinguish between the serious adverse events related to the investigational device, those related to the procedures (any procedure specific to the clinical investigation), and those unrelated to either the investigational device or study procedures. An adverse event can be related both to procedures and the investigational device.³³

Table 4. Causality of adverse events

	
Relationship to the device, comparator or procedures can be excluded when:
 
 – the event has no temporal relationship with the use of the investigational device, or the procedures related to application of the investigational device; – the serious adverse event does not follow a known response pattern to the medical device (if the response pattern is previously known) and is biologically implausible; – the discontinuation of medical device application or the reduction of the level of activation/exposure - when clinically feasible - and reintroduction of its use (or increase of the level of activation/exposure), do not impact on the serious adverse event; – the event involves a body-site or an organ that cannot be affected by the device or procedure; – the serious adverse event can be attributed to another cause (eg, an underlying or concurrent illness/ clinical condition, an effect of another device, drug, treatment or other risk factors); – the event does not depend on a false result given by the investigational device used for diagnosis³⁴, when applicable; 
In order to establish the non-relatedness, not all the criteria listed above might be met at the same time, depending on the type of device/procedures and the serious adverse event.

Possible	The relationship with the use of the investigational device or comparator, or the relationship with procedures, is weak but cannot be ruled out completely. Alternative causes are also possible (e.g. an underlying or concurrent illness/ clinical condition or/and an effect of another device, drug or treatment). Cases where relatedness cannot be assessed, or no information has been obtained should also be classified as possible.
Probable	The relationship with the use of the investigational device or comparator, or the relationship with procedures, seems relevant and/or the event cannot be reasonably explained by another cause.
Causal relationship	
The serious adverse event is associated with the investigational device, comparator or with procedures beyond reasonable doubt when:
 
 – the event is a known side effect of the product category the device belongs to or of similar devices and procedures;

³³ Complications caused by concomitant treatments not imposed by the clinical investigation plan are considered not related. Similarly, several routine diagnostic or patient management procedures are applied to patients regardless of the clinical investigation plan. If routine procedures are not imposed by the clinical investigation plan, complications caused by them are also considered not related.

³⁴ If an investigational device gives an incorrect diagnosis, the patient might, for example, receive an unnecessary treatment and incur all the risks that accompany that treatment, or might be incorrectly diagnosed with a serious disease. In other cases, the patient might not receive an effective treatment (thereby missing out on the benefits that treatment would confer) or might not be diagnosed with the correct disease or condition.

- the event has a temporal relationship with investigational device use/application or procedures;
 - the event involves a body-site or organ that
 - the investigational device or procedures are applied to;
 - the investigational device or procedures have an effect on;
- the serious adverse event follows a known response pattern to the medical device (if the response pattern is previously known);
 - the discontinuation of medical device application (or reduction of the level of activation/exposure) and reintroduction of its use (or increase of the level of activation/exposure), impact on the serious adverse event (when clinically feasible);
 - other possible causes (eg, an underlying or concurrent illness/ clinical condition or/and an effect of another device, drug or treatment) have been adequately ruled out;
 - harm to the subject is due to error in use;
 - the event depends on a false result given by the investigational device used for diagnosis³⁵, when applicable;

In order to establish the relatedness, not all the criteria listed above might be met at the same time, depending on the type of device/procedures and the serious adverse event.

The Sponsor is responsible for the classification of adverse events and ongoing safety evaluation of the clinical investigation. The Sponsor or Sponsor's designee (Medical Monitor/Expert³⁶) shall review the Investigator's assessment of all adverse events and determine and document in writing their seriousness and relationship to the investigational device and the procedure; in case of disagreement between the Sponsor and the Investigator(s), BrainQ Technologies Ltd. shall communicate both opinions to concerned parties³⁷ (refer to § 8.3.6 for details on reporting of serious adverse events), unless otherwise instructed by a local regulation or guidance.

³⁵ If an investigational device gives an incorrect diagnosis, the patient might, for example, receive an unnecessary treatment and incur all the risks that accompany that treatment, or might be incorrectly diagnosed with a serious disease. In other cases, the patient might not receive an effective treatment (thereby missing out on the benefits that treatment would confer), or might not be diagnosed with the correct disease or condition

³⁶ Clinical Data Interchange Standards Consortium (CDISC) glossary item C51836 defines Medical Monitor as “A sponsor representative who has medical authority for the evaluation of the safety aspects of a clinical trial.” The US FDA Compliance Program 7348.810 BIORESEARCH MONITORING Guidance for FDA Staff on “SPONSORS, CONTRACT RESEARCH ORGANIZATIONS AND MONITORS” (April 2017) clarifies that Medical Monitor may have the responsibility for medical aspects of the study (and may be a physician) while other Monitors may assess regulatory compliance. ICH GCP E6(R2) defines medical expert as medical personnel who will be readily available to advise on trial related medical questions or problems.

ISO 14155:2020 notes that medical expertise is provided by a person qualified by education, training and experience, who is readily available to advise on the clinical investigation and related medical questions or problems. If necessary, outside consultant(s) can be available for this purpose.

³⁷ § 8.2.5(a) of EN ISO 14155:2011/AC:2011 and § 9.2.5(a) of ISO 14155:2020, and MEDDEV 2.7/3 revision 3

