Study Population:	The study will enroll up to 150 adult patients with subacute ischemic stroke, with a moderate to severe disability which includes an upper extremity motor impairment, who will be assigned (1:1 allocation ratio) to either active or sham study intervention using BQ 2.0, initiated 4-21 days after the index stroke event. Following the interim analysis, the sample size may be increased up to 344 subjects. Total enrollment from each site to be no more than 20% of the total sample size.
Study Description:	
The study intervention will be initiated 4-21 days after the index stroke event and will consist of a total of 45 sessions over a period of 9 weeks (5 treatments per week). Each session will last 60 minutes during which 40 consecutive minutes of active or sham study intervention using BQ 2.0 will be administered. Each study group will be guided by the BQ 2.0 application and asked to perform a standardized, pre-defined and evidence-based physical and occupational therapy regimen concurrent with the study intervention. The PT/OT regimen applied in both treatment and sham controlled groups is aligned with the Class 1 level A recommendation for patients with stroke to participate in a home-based rehabilitation program.¹
 
BQ 2.0 does not produce any noticeable sound, light or sensation in connection with the stimulation which may disclose the arm assignment, making it ideal for testing in a sham-controlled setup. During sham treatment sessions, for purposes of maintaining the blind, the device will function as if it is delivering the therapy (i.e., the device will turn on and all indicators will function), but the frequency and intensity parameters that are not visible to the subject or site study members will be set to zero so that no stimulation is delivered.
 
Screening phase
 
Prospective subjects, who are 3 to 21 days post-stroke, will be consented to participate in the study at either:
 
 a) a participating ACH, prior to anticipated transfer to a participating IRF, SNF, outpatient, or home setting; or b) at a participating IRF, SNF, outpatient, or home setting.

¹ Winstein CJ, Stein J, Arena R, et al. Guidelines for Adult Stroke Rehabilitation and Recovery. *Stroke* 2016; 47: e98–e169.

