2.3 RISK/BENEFIT ASSESSMENT

2.3.1 KNOWN POTENTIAL RISKS

To date, there have been no device- or procedure related events in the clinical trials sponsored by BrainQ Technologies Ltd.

The intensity of the BQ 2.0 is in the range of up to 1 Gauss, well below known safety thresholds, and the frequencies used are in the range of those normally observed in the human neural system (65). The device is similar in its field characteristics to pulsed electromagnetic field devices, including commercial home devices. These FDA approved or CE-marked devices use a similar or wider range of intensities and frequencies as the BQ 2.0. Examples of such devices are: Curatron-2000-HT (Curatronic Ltd., Jerusalem, Israel), indicated for treatment of acute and chronic pain as well as rheumatic disorders (mT range [mT = 10 G], frequency 1 –50 Hz), PhysioStim (Orthofix Medical Inc., Lewisville, TX, USA), indicated for treatment of nonunion fractures, and CervicalStim (Orthofix Medical Inc., Lewisville, TX, USA), indicated as an adjunct to cervical fusion surgery in patients at high-risk for non-fusion (1 Hz – 50 KHz, 2-G range), and IMRS (Swiss Bionic Solutions USA Inc., Cooper City, FL, USA), for energy and wellness (mT range, 0.5 –25 Hz). These and similar devices have been used and approved for many years (66-68). Furthermore, the BQ 2.0 intensity is significantly lower than approved stimulation devices, such as transcranial magnetic stimulation which often use fields of 1 – 1.5 T (10 000 – 15 000 G). An example of such a device is BrainsWay (BrainsWay, Jerusalem, Israel), FDA-cleared for a variety of psychiatric indications, and CE-marked for a variety of psychiatric and neurological treatments, including post-stroke rehabilitation.

Potential risks have been identified during risk analysis which included assessment of risks related to the design of the device and evaluation of peer-reviewed clinical evidence on the state of the art in treatments involving or devices utilizing generation of electromagnetic fields.

The following risks may occur during use of the device:

- During the PT session
 - o Fatigue during therapy;
 - o Pain during therapy;
 - o Fractures or abrasions (eg, cuts or bruises) sustained as a result of a fall during lower extremity PT exercises;
- Transient neurological events due to exposure to electromagnetic fields
 - o Paresthesia (tickling, numbing sensation in the skin);
 - o Phosphenes (seeing light);

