
 - To characterize the safety profile of the BQ therapy. - To show that the BQ 2.0 performs reliably. 	
 - Serious procedure or device related adverse events. - device deficiencies to detect operational reliability. 	
Tertiary/Exploratory		

 - To show that the BQ therapy is effective in reducing cognitive impairment, depression and fine-grained level of disability at 3 months post-stroke, when initiated 4 to 21 days following an ischemic stroke. - To characterize the long-term effect at 6 months post-stroke of the BQ therapy effect on upper limb functionality and health-related quality of life (HRQoL). - To formally evaluate the cost-effectiveness of the BQ therapy over a lifetime horizon from the perspective of the United States healthcare system. - To explore the relationship between adherence to treatment as measured by the Qompass and clinical outcomes 	
 - Montreal Cognitive Assessment (global cognitive function) – at 90 days post-stroke. - Patient Health Questionnaire-8 (depression) – at 90 days post-stroke. - Academic Medical Center Linear Disability Scale (granular level of disability) at 90 days post-stroke. - Modified Rankin Scale (global disability) change from baseline (4-21 days post-stroke) to 180 days post-stroke. - Stroke Impact Scale Hand Domain (patient-reported hand function) – change from baseline (4-21 days post-stroke) to 180 days post-stroke. - 5-level EQ-5D (health-related quality of life) at 180 days post-stroke. - Formal cost-effectiveness analysis over a lifetime horizon from the perspective of the United States healthcare system. - Relationship between adherence to treatment as measured by the Qompass and the clinical outcomes 	

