6.1.1.5 FREQUENCY OF EXPOSURE

The BQ 2.0 will be used 5 times a week to a total of 45 treatment sessions in each subject.

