9.4.4 SAFETY ANALYSES

Descriptive statistics will be presented per study group for all safety parameters.

The primary safety variable, the cumulative incidence (and 95% CI) of adverse events (AEs) reported throughout the study in each of the study groups, will be presented in tabular format and will include incidence tables by severity and relationship to study device and/or procedure.

Adverse event rates will be compared between the study groups with a Fisher's exact test.

Serious adverse events will be listed and discussed individually.

Treatment tolerability will be presented. The number and percent of subjects who fail to complete the study and the number and percent of subjects who fail to complete the study because of adverse events will be presented.

In addition, listings of all safety measures and device deficiencies will be produced.

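### Section 8.3.3.2 defines procedure-related adverse events in two incompatible ways, so procedure-only events after the first session could be labelled unrelated and left out of the safety endpoint

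*Protocol*

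**What the plan says.** The protocol's safety endpoint (section 3; the synopsis has the same) is "Serious procedure or device related adverse events". Who counts depends on how an event is classified under section 8.3.3.2, and that section describes the procedure category twice.

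- **Footnote 31**, attached to the investigator's causality assessment of every collected adverse event: "Procedure related events refers to the procedure related to the initial application of the investigational medical device only". It goes on: "and therefore not to any other procedures or treatments applied later throughout the clinical investigation", and gives treatment of adverse events as an example.
- **Body text**, addressed to both the Sponsor and the Investigators, which separates device-related serious events from "those related to the procedures (any procedure specific to the clinical investigation").

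The classification is then used in the analysis. Section 9.4.4 says the adverse event presentation "will include incidence tables by severity and relationship to study device and/or procedure". Section 8.3.8 makes 24-hour reporting of non-serious Grade 3 or higher events depend on a possible, probable or causal relationship to the device and/or the procedure.

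On exposure, section 6.1.1.5 states: "The BQ 2.0 will be used 5 times a week to a total of 45 treatment sessions in each subject". Sections 8.1.1.3 and 8.1.1.5 put device-guided physical and occupational therapy into every session, with about 30 minutes for the lower extremity. Section 2.3.1 lists fatigue and pain during therapy among the risks, and also "Fractures or abrasions (eg, cuts or bruises) sustained as a result of a fall during lower extremity PT exercises".

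**The concern.** The two statements cannot both govern. The footnote's wording suits a device that is applied once, such as an implant, where the application is the procedure. Here the device is put on again at each session and the plan imposes exercise alongside it, so procedural risk recurs throughout the treatment period.

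Take a fall with a fracture during in-session leg exercise in session 30, judged to be caused by the exercise and not by the device. Under the body text it is related to a procedure specific to the investigation, and it counts in the endpoint if serious. Under footnote 31, read as written, it arose from something applied after the initial application and is not procedure related. The same event gets two labels, depending on which sentence the rater follows.

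At stake are the endpoint count, the relationship breakdown in 9.4.4, and, for non-serious Grade 3 or higher events, whether 8.3.8 requires a report.

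**Working it through.** No power or alpha calculation bears on this. The check is a comparison of passages and a count of sessions.

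**1. Which scope does the rest of the protocol support?**

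| Place | Scope of the procedure category |
|---|---|
| 8.3.3.2, footnote 31 | Initial application of the device only; later procedures and treatments excluded |
| 8.3.3.2, body | Any procedure specific to the investigation |
| 8.3.3.2, footnote 33 | Excludes concomitant treatments and routine procedures that the plan does not impose |
| 8.3.3.2, Table 4 | Device use or application, and procedures, with no restriction to the first |
| 8.3.1, adverse event definition | Events related to the procedures involved, without restriction |

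The in-session exercise is imposed by the plan (6.1.2, 8.1.1.3, 8.1.1.5), so footnote 33 does not exclude it. Footnote 31 is the only one of the five that would.

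**2. How many sessions does each scope cover?**

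Inputs: 9 weeks and 5 sessions a week (synopsis: "a total of 45 sessions over a period of 9 weeks (5 treatments per week")); 150 subjects randomized, or up to 344 after the interim analysis (synopsis; 9.2; 9.4.6).

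- Planned sessions per subject: 9 × 5 = 45, which reproduces the protocol's figure.
- Body text: 45 of 45 sessions covered.
- Footnote 31, reading the initial application as session 1: 1 of 45 covered (1/45 = 2.2%).
- Sessions left out: 45 − 1 = 44 (44/45 = 97.8%).

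Both arms belong in the total, because sham subjects wear the device and do the same exercises (6.1.2, 6.1.3). With every session delivered:

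| Randomized | All sessions (N × 45) | Outside footnote 31 (N × 44) |
|---|---|---|
| 150 | 6,750 | 6,600 |
| 344 | 15,480 | 15,136 |

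**3. What these figures measure.** They count sessions, not events. The protocol gives no rate for serious events caused by the procedure alone, so the number of misclassified events cannot be derived from it.

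**4. Which events are exposed?** An event changes label only if it (a) is related to a study procedure, (b) is not also judged related to the device, (c) occurs outside the initial application, and (d) is assessed by someone applying footnote 31 literally.

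**The case against.** The strongest reply is that the footnote means something narrower. Its example is treatment of adverse events, so it may be meant to separate applying the device from later medical care, and not session 1 from sessions 2 to 45. That is a plausible intention, and it is why 44 of 45 is a worst case. But the example is only an illustration. The operative words limit the category to the initial application and exclude what is applied later, and a rater has only those words.

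Other safeguards also stand:

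- **Device route.** The endpoint counts events related to the procedure or the device. Section 2.3.1 presents the therapy-session risks as ones that may occur during use of the device, and 8.3.1 defines an adverse device effect by relation to device use. Some exercise falls would therefore be classed as device related, and footnote 31 would not touch them. This narrows the gap but does not close it, since 8.3.3.2 treats device and procedure as separate categories.
- **Central review.** The Sponsor or Medical Monitor reviews every causality assessment and documents relationship in writing (8.3.3.2). This can even out differences between sites, but the reviewer works from the same two definitions.
- **No lost events.** All adverse events are documented whatever their relationship (8.3.5), serious ones are reported within 24 hours without a relatedness condition (8.3.6), and 9.4.4 compares overall adverse event rates and discusses serious events individually. Only the label is exposed.

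A reader might infer that related events will certainly be undercounted, or that the study-wide halt in 10.1.2 would fail to trigger. The documents support neither. Some raters will follow the body text. The halt rule refers to a probable or causal relationship without naming a procedure category, so its link to footnote 31 is indirect, and a suspicion of unacceptable risk leads to suspension separately.

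**Conclusion.** The contradiction is real and should be resolved. As written, footnote 31 would give the wrong label to a procedure-only event after the first session, measured against the definition that the body, footnote 33 and Table 4 share. The result may be an undercount in the serious procedure- or device-related endpoint, in the 9.4.4 relationship tables and among events reportable under 8.3.8.

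The size is bounded, not estimated. At most 44 of 45 sessions per subject (97.8%) fall outside the footnote, assuming that initial application means the first session and that all sessions are delivered. It would be wrong to read this as 97.8% of events lost or misclassified. The number of events affected is unknown and could be small, because device-related events count at every session and no event leaves the database.

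The primary efficacy analysis and the overall adverse event comparison are unaffected. Subjects and investigators are blinded and both arms follow the same session procedures, so nothing in the documents suggests that mislabelling would favour one arm. The problem is a safety endpoint with two definitions, not a demonstrated bias.

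**What to change.** Delete footnote 31. Alternatively, reword it so that it excludes only treatments the investigation plan does not impose, such as treatment given for an adverse event, which would bring it into line with footnote 33.

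Then use the body definition throughout: procedure related means related to any procedure specific to this investigation, including every device application and the intra-session physical and occupational therapy at any of the 45 sessions, in both arms. Apply that one definition to the safety endpoint in section 3 and the synopsis, to Table 4, and to the CRF and its completion guidance. Relationship assessments already made should be checked against it.

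The cost is one footnote, the CRF guidance and a check of existing causality entries. No assessment, visit or sample size changes. The count of related events may become slightly less favourable.
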